#### **9.4. Exploratory Efficacy Endpoints and Analyses**

All exploratory analyses will be performed on the ITT Population unless otherwise specified. For the exploratory efficacy endpoint analysis of continuous variables, a mixed model repeated measures (MMRM) analysis of covariance (ANCOVA) model will be fit to the individual change from baseline value for the parameter of interest, with terms for baseline score, tophi presence at baseline, and factors of treatment group, visit, visit by treatment group interaction and visit by baseline interaction. The Post Treatment Follow-up Month 3 and Month 6 visits will not be included in the MMRM model. The unstructured (UN) variance-covariance matrix will be used. In the event that this matrix does not allow for model convergence, the following three variance-covariance matrices will be attempted in order until one converges: heterogeneous Toeplitz (TOEPH), heterogeneous compound symmetry (CSH), and Toeplitz (TOEP). The p-values for all terms in the model will be presented, as well as the treatment group LS means and associated SE, and their difference, SE of the difference, 95% CIs and p-value, overall and at each visit.

P-values for exploratory endpoints will be provided for descriptive purposes only.

No imputation of missing data will be performed for the exploratory analysis of continuous variables, as the analysis will be performed using MMRM models, which accommodate missing data and allow information from every visit to contribute to the analysis of the data. The only exception to this is that for any subject in the ITT Population without post-baseline values (unless “Site Closure”), a change from Baseline value of 0 will be imputed at the first post-baseline visit (in order to avoid exclusion from the MMRM analysis). Subjects with no post-

baseline assessments due to site closure will be excluded from analysis. Otherwise, all available data for subjects impacted by COVID-19 will be included.

For exploratory efficacy endpoint analysis of categorical variables, either CMH or chi-square test (for endpoints related to tophi) will be used.

Observed efficacy endpoints will be summarized by pegloticase treatment status (On Treatment, Post-Treatment, and Overall), visit, and treatment group. On Treatment will include post-baseline visits on or after pegloticase infusions. Subjects will only be summarized in the On Treatment visits for visits that occur (and results available) while still receiving pegloticase infusions. End of pegloticase infusion visit (windowed) if occurs, will also be considered On Treatment, as well as the Week 52 visit for subjects who complete treatment and study at Week 52. Post-Treatment visits are any post-baseline visits after the end of pegloticase infusions (or Week 52/EOS if subject completes treatment). Overall status will include all visits for all subjects regardless of pegloticase treatment status.

#### 9.4.1. Change from Baseline in Urate Deposition Volume and Bone Erosion using DECT

For sites with DECT capability, and subjects who provide consent, an optional DECT (hands, feet, knees and other anatomical areas as clinically indicated) will be obtained at Day 1 and Weeks 14, 24 and at the End of Pegloticase Infusions Visit (if applicable) and the Week 52/End of Study/Early Termination Visit. The DECT on Day 1 must be completed prior to the infusion and may be completed within the 14 days prior to Day 1. The DECT at all other scheduled timepoints may be completed within +/- 10 days of the scheduled timepoint.

Subjects who end pegloticase infusions prior to Week 52 should follow the scheduled timepoints but avoid a repeat DECT scan within 6 weeks of a prior scan (detailed guidance is provided with the imaging manual).

CT scans of the hands and feet have been used to assess erosive damage in the small joints of the hands and feet in rheumatoid arthritis and gout. The DECT images will be used to assess erosion change using published semiquantitative scoring systems. Erosion scoring in the hand will follow the OMERACT RAMRIS score, which assesses erosive change in 10 locations in each hand and 15 locations in each wrist. Erosive damage at each location is scored from 0 to 10, with each score representing 10% incremental loss of each carpal bone or the peripheral 1 cm of articular bone for long bones (radius, ulna, metacarpals and phalanges). The total erosion score can range from 0 to 250 for each hand. Erosion scoring in the foot will follow the method published by Dalbeth et al [4] which was based on the OMERACT RAMRIS score. Erosive damage at each location is scored from 0 to 10, as in the hand. The total erosion score can range from 0 to 70 for each foot.

The observed values and the change from baseline for urate deposition volume and bone erosion scores at each scheduled visit will be summarized using descriptive statistics (i.e. n, mean, standard deviation, median, minimum, and maximum). The baseline is defined as the last non-missing measurement before the first pegloticase infusion. Changes from baseline for urate deposition volume and bone erosion score to each visit and overall will be analyzed with MMRM ANCOVA model as described in Section 9.4.

### Analysis of Change from Baseline in Bone Erosion using X-Rays

The observed values and the change from baseline for bone erosion score at each scheduled visit will be summarized using descriptive statistics (i.e. n, mean, standard deviation, median, minimum, and maximum). The baseline is defined as the last non-missing measurement before the first pegloticase infusion. Changes from baseline for bone erosion scores to each visit and overall will be analyzed with an MMRM ANCOVA model as described in [Section 9.4](#).

#### 9.4.3. Proportion of Subjects with Complete Resolution of $\geq 1$ Tophi at Weeks 24 and 36 with Tophi at Baseline

The proportion of complete resolution of  $\geq 1$  tophi at Weeks 24 and 36 will be calculated using the same method used for Week 52 ([Section 9.3.2](#)). The difference in the proportion of subjects with resolution of  $\geq 1$  tophi at Weeks 24 and 36, overall response at each visit, and best overall response between pegloticase with MTX and pegloticase with placebo will be tested with a chi-square test, and the difference in rates will be estimated along with the corresponding 95% CI and p-value.

#### 9.4.4. Change from Baseline in Tophus Size using Digital Photography in Subjects with Tophi at Baseline

Digital photography is used to assess tophus size (long axis measured using digital photography, see [Section 9.3.2](#)) at the Week -6 (prior to the first dose of MTX) Visit during the MTX Tolerability Assessment Period; prior to pegloticase infusion at Day 1 and Weeks 14, 24, and 36, and Visits during the Pegloticase + IMM Period; and at the End of Pegloticase Infusions Visit (if applicable), Week 52/End of Study/Early Termination Visit, Post Treatment Follow-up Month 3, and Post-treatment Follow-up Month 6.

The long axis will be summed over all measurable tophi at each visit. The observed values, the change from baseline, and the percentage change from baseline for the sum of the long axis at each scheduled visit will be summarized using descriptive statistics (i.e. n, mean, standard deviation, median, minimum, and maximum). Only tophi that are measured at baseline and each post-baseline visit (or new tophi that appear after baseline) will be included in the analysis. If a tophus measured at baseline is unable to be evaluated at a post-baseline visit (e.g. due to poor image quality), the last available measurement (including baseline) will be carried forward in order to calculate the sum of longest diameters over all tophi. If no assessment was performed or all baseline tophi are unable to be evaluated at a post-baseline visit, tophi size will be missing for that visit. Changes from baseline for tophus size to each visit and overall will be analyzed with an MMRM ANCOVA model as described in [Section 9.4](#).

This document is confidential.

#### 9.4.5. Proportion of Month 9 Responders

The proportion of Month 9 (Weeks 32, 34, and 36) responders, will be defined as subjects achieving and maintaining sUA < 6 mg/dL for at least 80% of the time during Month 9.

This endpoint will be analyzed for the ITT population.

This determination will be completed using the same linear interpolation method described for the primary efficacy endpoint in Section 9.2.1. The Month 9 period will include pre-infusion and post-infusion results at Week 32, pre-infusion and post-infusion results at Week 34, pre-infusion results at Week 36, and unscheduled assessments of sUA collected between Week 32 and Week 36 processed by the central laboratory. Section 9.1 shows the rules for inclusion of sUA values reported by local laboratories.

If the subject's proportion of hours where sUA was less than 6 mg/dL, P, is greater than or equal to 80% the subject will be called a responder for the Month 9 responder endpoint. Subjects meeting the stopping rule, i.e. has pre-infusion sUA values greater than 6 mg/dL at 2 consecutive scheduled visits (starting at Week 2) through Week 36 will be counted as non-responders. Subjects with the proportion of hours, P, less than 80% will be counted as non-responders.

There will be no imputation of sUA values due to missing values among those collected between Week 32 and Week 36, unless missing data is due to site closure. At least two sUA observations from different visits must be available in order for a subject to be eligible for consideration as a responder. Subjects with only one sUA observation will be considered a non-responder, regardless of the value of that single observation. For subjects with "Site Closure" missing data during Month 9, the rules described in Section 6.3.3 will be applied. The proportion of Month 9 responders will be analyzed using the same multiple imputation method and the stratified weighting approach specified for primary analysis of the primary endpoint.

In addition, the proportion of responders along with a 95% confidence interval for the proportion will be summarized based on the observed data (i.e. with no imputation based on COVID-19 impact), with non-responder imputation used for subjects who meet the stopping rule or have missing results during Month 9 (this will be the primary analysis method if there are no "Site Closure subjects").

The proportion of hours during the period where the sUA was less than 6 mg/dL (based on observed sUA) will be summarized using descriptive statistics (i.e. n, mean, standard deviation, median, 25th quartile, 75th quartile, minimum, and maximum). The number and proportion of subjects that discontinued treatment due to the stopping rule will be summarized. The number and proportion of responders will be summarized along with a 95% exact (Clopper-Pearson) CI for the proportion. In addition, the number and proportion of subjects with data available at Week 36 responder, data available at Week 36 non-responder (subcategories of met stopping rule at or before Week 36, did not meet stopping rule), and data not available at Week 36 non-responder (subcategories of met stopping rule at or before Week 36, missing data for other reason) will be summarized.

The proportion of sUA < 6 mg/dL responders during Month 9 will be plotted.

#### 9.4.6. Proportion of Month 3 Responders

The proportion of Month 3 (Weeks 10, 12, and 14) responders, will be defined as subjects achieving and maintaining sUA < 6 mg/dL for at least 80% of the time during Month 3.

This determination will be completed using the same linear interpolation method described for the primary efficacy endpoint in Section 9.2.1. The Month 3 period will include pre-infusion and post-infusion results at Week 10, pre-infusion and post-infusion results at Week 12, pre-infusion results at Week 14, and unscheduled assessments of sUA collected between Week 10 and Week 14 processed by the central laboratory. Section 9.1 shows the rules for inclusion of sUA values reported by local laboratories.

If the subject's proportion of hours where sUA was less than 6 mg/dL, P, is greater than or equal to 80% the subject will be called a responder for the Month 3 responder endpoint. Subjects meeting the stopping rule, i.e. has pre-infusion sUA values greater than 6 mg/dL at 2 consecutive scheduled visits (starting at Week 2) through Week 14 will be counted as non-responders. A subject with the proportion of hours, P, less than 80% will be counted as non-responders. In addition to stopping rule, a subject who withdraws from study treatment for any reason other than the stopping rule after randomization and prior to or during Month 3 will be considered a non-responder at the time of withdrawal (and for all subsequent time points) if sUA values are not collected at the planned time points.

There will be no imputation of sUA values due to missed collections among those collected between Week 10 and Week 14, unless missing data is due to site closure. At least two sUA observations from different visits must be available in order for a subject to be eligible for consideration as a responder. Subjects with only one sUA observation will be considered a non-responder, regardless of the value of that single observation. For subjects with "Site Closure" missing data during Month 3, the rules described in Section 6.3.3 will be applied. The proportion of Month 3 responders will be analyzed using the same multiple imputation method and the stratified weighting approach specified for primary analysis of the primary endpoint.

In addition, the proportion of responders along with a 95% confidence interval for the proportion will be summarized based on the observed data (i.e. with no imputation based on COVID-19 impact), with non-responder imputation used for subjects who meet the stopping rule or have missing results during Month 3 (this will be the primary analysis method if there are no "Site Closure subjects").

The proportion of hours during the period where the sUA was less than 6 mg/dL (based on observed sUA) will be summarized using descriptive statistics (i.e. n, mean, standard deviation, median, 25th quartile, 75th quartile, minimum, and maximum). The number and proportion of subjects that discontinued treatment due to the stopping rule will be summarized. In addition, the number and proportion of subjects missing all data in analysis period, with only one measurement (above cutoff) in analysis period, and with only one measurement (below cutoff) in analysis period will be summarized. The number and proportion of responders and non-responders will be summarized. In addition, the number and proportion of subjects with data available at Week 14 responder, data available at Week 14 non-responder (subcategories of met stopping rule at or before Week 14, did not meet stopping rule), and data not available at

Week 14 non-responder (subcategories of met stopping rule at or before Week 14, missing data for other reason) will be summarized.

The proportion of sUA < 6 mg/dL responders during Month 3 will be plotted.

#### 9.4.7. Proportion of Overall Responders Month 3 and Month 6 Combined

The proportion of overall responders through Month 6 is defined as subjects achieving and maintaining sUA < 6 mg/dL for at least 80% of the time during Months 3 and 6 combined. See Section 9.2.1 for the sUA results included in Month 6. See Section 9.4.6 for the sUA results included in Month 3. Section 9.1 shows the rules for inclusion of sUA values reported by local laboratories.

The definition of overall responders through Month 6 is dependent on the number of available sUA results available during Month 3 and during Month 6.

Case	Number of sUA Values at Month 3	Number of sUA Values at Month 6	Overall Response Determination
1	Any Number	$\leq 1$	Declared Overall Non-responder
2	$\leq 1$	Any Number	Declared Overall Non-responder
3	> 1 Record	> 1 Record	Overall Response is defined based on the weighted proportion of hours below the sUA < 6 mg/dL cutoff. See the remainder of this section.

Let T1 = the number of elapsed hours between the first and last non-missing sUA concentration among those collected between pre-infusion Week 10 and pre-infusion Week 14 collections.

Let T2 = the number of elapsed hours between the first and last non-missing sUA concentration among those collected between pre-infusion Week 20 and pre-infusion Week 24 collections.

Let W1 = the number of hours among the T1 hours where the sUA concentration was below 6 mg/dL.

Let W2 = the number of hours among the T2 hours where the sUA concentration was below 6 mg/dL.

$$\text{The proportion of hours } P = 100 * \frac{W_1 + W_2}{T_1 + T_2}$$

This is the weighted proportion of hours below 6 mg/dL.

If the subject's proportion of hours, P, is greater than or equal to 80% the subject will be called a responder for the overall responder endpoint. A subject with the proportion of hours, P, less than 80% will be counted as non-responders.

Subjects meeting the stopping rule, i.e. has pre-infusion sUA values greater than 6 mg/dL at 2 consecutive scheduled visits (starting at Week 2) through Week 24 will be counted as overall non-responders.

The proportion of hours during the period where the sUA was less than 6 mg/dL will be summarized using descriptive statistics (i.e. n, mean, standard deviation, median, minimum, and maximum). The number and proportion of subjects that discontinued treatment due to the stopping rule will be summarized. The proportion of responders during Month 3 and Month 6 combined will be analyzed using the same multiple imputation method (if performed) and the stratified weighting approach specified for primary analysis of the primary endpoint.

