#### 7.1.2 Pegloticase

[REDACTED]

Two replicate pivotal phase 3 studies for pegloticase were undertaken to establish the efficacy and safety of the product. The primary endpoint was defined as plasma UA (highly correlated to serum uric acid) reduction to below 6 mg/dL for 80% of the time in Months 3 and 6 combined. The pooled response rate for pegloticase 8 mg every two weeks was 42%, versus a placebo response rate of 0%. There was also a greater reduction in complete resolution of  $\geq 1$  tophus in the every 2 weeks dosing group, and favorable effect of pegloticase treatment in the reduction of the number of tender and swollen joints. In subsequent open-label extension studies, pegloticase led to continued control of pUA, reduction in gout flares, and continued resolution of tophi, suggesting continuing benefit with extended pegloticase treatment beyond the initial 6 months of therapy, particularly in subjects who met responder criteria in the placebo-controlled trials.

In the phase 3 pivotal studies, deaths, AEs, SAEs, as well as the laboratory abnormalities were generally equally distributed across placebo and pegloticase treatment groups, with the clear exception of gout flares and infusion reactions. Pegloticase-treated subjects exhibited a higher rate of gout flares during Months 1-3 as uric acid was being acutely lowered, then a decrease in gout flares vs. placebo during Months 4-6. Despite use of prophylactic medications against hypersensitivity including administration of corticosteroids, antihistamine, and acetaminophen in advance of each pegloticase infusion, infusion reactions were seen in 22/85 (26%) of subjects

receiving the 8 mg 2 week regimen. There was no specified definition of anaphylaxis in the Phase 3 protocols, and there were no investigator-reported events of anaphylaxis in the Phase 3 studies with pegloticase. However, in a post-hoc review applying the NIAID/FAAN criteria (Sampson et al., 2006), it was determined that across the Phase 2 and Phase 3 program, anaphylaxis occurred in 6.5% of subjects treated with pegloticase dosed every 2 weeks. Anaphylaxis generally occurred within 2 hours after treatment. Manifestations included wheezing, peri-oral or lingual edema, or hemodynamic instability, with or without rash or urticaria. All of these events had relatively rapid resolution with the cessation of infusion.

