#### **9.2.1. Calculation of Response**

The sUA concentrations vs. time (collected to the nearest minute in the CRF) curve will be used to estimate the proportion of time that the sUA is < 6 mg/dL using the available pre-infusion (or values at visit when no infusion performed) and post-infusion samples with non-missing sUA values.

The Month 6 period will include pre-infusion and post-infusion results at Week 20, results at Week 21, pre-infusion and post-infusion results at Week 22, results at Week 23, and pre-infusion results at Week 24, and unscheduled assessments of sUA collected between Week 20 and Week 24

This document is confidential.

processed by the central laboratory. Results from visits where an infusion was not performed (e.g. subject discontinued pegloticase but remained in study) will be used when available. Section 9.1 shows the rules for inclusion of sUA values reported by local laboratories.

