### 9.2.2. Handling of Missing Data and Multiple Imputation Process

At least two sUA observations from different visits during Month 6 must be available in order for a subject to be eligible for consideration as a responder. Subjects with only one sUA observation will be considered non-responders, regardless of the value of that single observation; subjects with no sUA values will also be considered non-responders. In addition, subjects who meet the stopping rule (sUA values > 6 mg/dL at 2 consecutive scheduled visits (excluding post-infusion sUA) starting at Week 2 prior to or during Month 6 will be considered to be non-responders. For determination of stopping rule, as specified in Section 9.1, if both central lab and local lab sUA results are available at a visit then the central lab value will be used for stopping rule determination. For subjects with missing data due to COVID-19 that is not “Site Closure”, there will be no imputation of sUA values due to missing values among those collected between Week 20 and Week 24.

For subjects with missing data due to site closure (due to COVID-19 as defined in Section 6.3.3) during Month 6 (i.e. have < 2 visits during Month 6 with sUA available), multiple imputation will be used to impute missing sUA values .

The multiple imputation process for imputing missing sUA will involve the following steps:

- 1) For subjects who met the stopping rule and have missing data prior to or during Month 6, last observation carried forward (LOCF) imputation will be done in order to prevent the

This document is confidential.

multiple imputation algorithm from imputing data inconsistent with known information. For example, subjects who meet the sUA stopping rule and have missing sUA after stopping rule is met would be expected to continue to have sUA > 6 mg/dL in the absence of other treatment, and thus would be expected to be non-responders. LOCF is used to provide complete data for stopping rule subjects that may be used to impute missing sUA for "Site Closure" subjects. Note that these LOCF values will only be used in the imputation model, and will be excluded from all analyses once the imputation model has been used.

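### The Months 3 and 6 combined responder endpoint counts sUA records rather than visits, so one visit's pre- and post-infusion pair can stand for a whole month (minor; exploratory endpoint only)

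*SAP*

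**What the plan says.** SAP Section 9.4.7 states that the definition of overall response "is dependent on the number of available sUA results available during Month 3 and during Month 6". Its table has three cases. A subject with one value or none in either month is an overall non-responder. A subject with more than one record in both months falls in Case 3, where "Overall Response is defined based on the weighted proportion of hours below the sUA < 6 mg/dL cutoff".

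That proportion is P = 100 × (W1 + W2)/(T1 + T2), and a subject with P of at least 80% is a responder. The denominators cover only the observed span: "Let T2 = the number of elapsed hours between the first and last non-missing sUA concentration" among the Month 6 samples, and likewise T1 for Month 3. W1 and W2 are the hours below 6 mg/dL within those spans.

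On which samples count, 9.4.7 says "See Section 9.2.1 for the sUA results included in Month 6". Section 9.2.1 in turn says "The Month 6 period will include pre-infusion and post-infusion results at Week 20, results at Week 21", and treats Week 22 the same way. The two samples of one infusion visit are therefore separate results.

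The single-month endpoints carry a further condition. For Month 6, Section 9.2.2 says "At least two sUA observations from different visits during Month 6 must be available in order for a subject to be eligible". For Month 3, Section 9.4.6 says "At least two sUA observations from different visits must be available in order for a subject to be eligible for consideration as a responder". Sections 9.3.1 (Month 12) and 9.4.5 (Month 9) set the same condition. Section 9.4.7 neither repeats it nor cites 9.2.2. Its closing paragraph carries over only the multiple imputation method and the stratified weighting.

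**The concern.** Weeks 20 and 22 in Month 6, and Weeks 10 and 12 in Month 3, each yield a pre- and a post-infusion sample. One such visit supplies two records, which is all that Case 3 asks for. The month then enters the formula with a span of hours instead of about four weeks, and the other month determines P almost alone.

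A subject could therefore be counted as having kept urate below 6 mg/dL over Months 3 and 6 when the only Month 6 evidence is one visit with both values above 6 mg/dL. The stopping-rule override in 9.4.7 does not catch this by itself, because it needs elevated values at two successive scheduled visits. At stake is the accuracy of the combined response rate and its consistency with the other sUA responder endpoints. Section 9.2.5 restates the different-visits condition and leaves its removal to a possible post-hoc analysis, so the condition looks deliberate.

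**Working it through.** **Inputs**
- Full four-week window: 672 h. SAP 9.2.2 gives this for Month 6, and it reproduces: 4 × 168 h = 28 × 24 h = 672 h. Week 10 to Week 14 has the same length, so a complete Month 3 has T1 = 672 h.
- Pre-infusion sample: up to 48 h before the infusion (SAP 9.1).
- Infusion: about 120 ± 15 minutes, so at most 2.25 h (Protocol 9.4.6.3.1.2).
- Observation afterwards: 1 h (Protocol 9.4.1.3).
- Post-infusion sample: any time between end of infusion and discharge (Protocol 9.5.8.2.11). Taking it about 1 h after the infusion is an assumption.
- Threshold: P ≥ 80% (SAP 9.4.7).

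Section 9.4.7 gives no worked figure of its own to reproduce.

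**Span of a single Month 6 visit**
- Both samples on the same day: 2 h infusion + 1 h = 3 h.
- Pre-infusion sample drawn as early as allowed: 48 + 2.25 + 1 = 51.25 h.

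**Score when both Month 6 values are above 6 mg/dL**
Linear interpolation between two values above 6 gives W2 = 0, so P = 100 × W1/(T1 + T2).

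| Month 3 | T2 = 3 h | T2 = 51.25 h |
|---|---|---|
| All below 6 (W1 = 672 h) | 672/675 = 99.6% | 672/723.25 = 92.9% |
| 90% below 6 (W1 = 604.8 h) | 604.8/675 = 89.6% | 604.8/723.25 = 83.6% |

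All four are responders under 9.4.7. With Month 3 fully controlled, P ≥ 80% holds whenever T2 ≤ T1/4 = 168 h. The smallest Month 3 share that still gives a responder is 0.8 × (672 + T2)/672, which is 80.4% at 3 h and 86.1% at 51.25 h.

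**Comparison**
If the same loss of control were observed over all of Month 6 (T2 = 672 h, W2 = 0), P would be 672/1344 = 50%, a non-responder. Under the different-visits condition of 9.2.2 and 9.4.6, the single-visit subject would be a non-responder whatever P is.

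**Weight of one subject**
With 45 and 90 subjects, 1/45 = 2.2 and 1/90 = 1.1 percentage points. With the 145 planned in SAP 3.6 (about 48 and 97), the weights are 2.1 and 1.0 points.

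**The case against.** The strongest reply is that the case is hard to reach. A reader might infer that any infusion reaction followed by stopping treatment produces it. The documents do not support that.
- Subjects who stop pegloticase stay on study. Protocol 9.5.8.3 requires on-site visits at Weeks 20 to 24 (9.3.3.1.1 encourages them). The End of Pegloticase Infusions and Early Termination visits each include an sUA sample.
- SAP 6.4, Table 1, assigns such a sample to Week 21 on days 145–151 and to Week 22 on days 152–158, and 9.2.1 uses visits without an infusion.
- A second value above 6 assigned to Week 21 would meet the stopping rule as 9.2.2 words it. One at day 155 gives T2 = 336 h and P = 672/1008 = 66.7%, a non-responder.
- If the preceding scheduled pre-infusion value was also above 6, the 9.4.7 override applies. COVID-19-related missing data go to non-response or imputation under 6.3.3.

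All of this stands, and it narrows the point to subjects with no further Month 6 value assigned to another visit. That means, for example, immediate loss to follow-up, skipped visits, or an end-of-treatment sample by day 144, which falls in the Week 20 window and yields to the scheduled data.

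It is also fair that an overall responder who is a Month 6 non-responder is no anomaly in itself. With complete data, 100% in Month 3 and 65% in Month 6 average 82.5% by design. The problem here is that Month 6 contributes only hours to the denominator.

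The rule that withdrawal counts as non-response does not clearly close the gap. Protocol 9.6.5.1 ties it to Months 6 and 12 for the primary and secondary endpoints. SAP 9.4.6 ties it to withdrawal before or during Month 3, and 9.4.7 does not repeat it.

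**Conclusion.** The rule in 9.4.7 is wrong as written, but the point is minor. Followed literally, it classes a subject with no Month 6 time below 6 mg/dL as an overall responder, with P between 92.9% and 99.6% when Month 3 is fully controlled. The conclusion assumes adequate Month 3 control, a preceding scheduled pre-infusion value not above 6 mg/dL, no later Month 6 value assigned to another visit, and missing data outside 6.3.3. It does not depend on the exact sample timing, since any T2 up to 168 h suffices with T1 = W1 = 672 h. The number of such subjects is not given and is probably small. Each is worth about 2 points in the placebo arm and 1 point in the MTX arm.

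Two stronger readings are not supported. First, the trial's main conclusions are not at risk: the primary and secondary endpoints have their own rules, and this endpoint is exploratory with descriptive p-values (SAP 9.4). Second, a reader might take the endpoint as the trial's formal link to the phase 3 studies, whose primary endpoint Protocol 7.1.2 describes as "reduction to below 6 mg/dL for 80% of the time in Months 3 and 6 combined". The documents never give it that role. The phase 3 measure was plasma urate, and no phase 3 missing-data rule is stated, so the effect on comparability cannot be judged.

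**What to change.** In the 9.4.7 case table, replace the entry ≤ 1 with: values from fewer than two different visits. Replace the entry for more than one record with: values from at least two different visits. Do this for both Month 3 and Month 6, and change the matching line in the derivation program. This applies the condition already used in 9.2.2 and 9.4.6.

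The cost is a few table cells and one line of code, with no new data. The overall response rate may come out slightly lower. The change is best made before unblinding.

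The edit leaves the span-based denominators as they are. Values only at Weeks 20 and 21, 168 h apart and both above 6, would give 672/840 = 80.0%, and the outcome would then depend on the stopping rule.
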